#### 11.1.2 Safety Endpoint 2: Major EMPOWER MPS System- and Procedure-related Complication-free Rate from Implant through 12 Months Post-Implant

Safety Endpoint 2 will be assessed for subjects who undergo any portion of the EMPOWER PG implant procedure. Safety will be confirmed by evaluating the Major EMPOWER MPS System- and Procedure-related CFR between the EMPOWER PG implant procedure date and 365 days (12 months) post-implant procedure date. The same definition of Major EMPOWER System- and Procedure-related Complication that was used for Safety Endpoint 1 (refer to **Section 11.1.1**) will also be used for Safety Endpoint

```
Page 84 of 148
```

2. This endpoint will support both the CE Mark and FDA's requirements for Post Market 1 submissions.

#### 11.1.2.1 Hypotheses

The following hypotheses will be used to evaluate Safety Endpoint 2 from implant through 12 months post-implant:

- H0: The Major EMPOWER MPS System- and Procedure-related CFR through 12 months is  $\leq 81\%$
- HA: The Major EMPOWER MPS System- and Procedure-related CFR through 12 months is > 81%

The performance goal was selected to be consistent with the initial recommendations for study of leadless cardiac pacemaker therapy, written by the Medicines & Healthcare Products Regulatory Agency (MHRA) Expert Advisory Group.

#### 11.1.2.2 Sample Size - CE Mark Cohort

Endpoint analysis will be performed on subjects that undergo an EMPOWER PG implant procedure, including subjects that do not have an EMPOWER PG successfully implanted. The CE Mark cohort analysis must include at least 112 subjects that underwent an EMPOWER PG implant procedure with data at 12 months to be sufficiently powered. Sample size estimates were obtained using the normal approximation to the binomial and verified through simulations based on Kaplan-Meier methodology using SAS 9.4; Kaplan-Meier methodology will be used for the analyses.

Sample size was calculated using the following assumptions:

- Performance goal =  $81\%^{37}$
- One-sided significance level = 2.5%
- Power = 90%

The sample size for this study was not determined by this endpoint.

#### 11.1.2.3 Sample Size - Post-Market 1 Cohort

The Post-Market 1 cohort analysis will be done on the full subject enrollment (n=300). Given a 30% attrition rate, it is expected that 210 subjects will be followed through 1 year. Using the normal approximation to the binomial method and the assumptions outlined below, the Post-Market 1 analysis will be powered at 99.8%.

• Performance goal = 81%

<sup>38 Leadless cardiac pacemaker therapy: design of pre- and post-market clinical studies. Recommendations from MHRA Expert Advisory Group. October 2018.

<sup>39 DCD / IEDB Improved Submission Paradigm for Leadless Cardiac Pacemakers (2015)

- One-sided significance level = 2.5%
- Attrition Rate = 30%

#### 11.1.2.4 Statistical Methods

Endpoint analysis will be performed on subjects that undergo an EMPOWER PG implant procedure, including subjects that do not have the EMPOWER PG successfully implanted (i.e., both implant and attempt subjects), using two different cohorts. The CE Mark cohort will consist of the minimum number of subjects required to evaluate this endpoint - 112 subjects who undergo an EMPOWER PG implant procedure and have been followed for 12 months. The FDA Post-Market 1 cohort will consist of all subject enrollments who undergo an EMPOWER PG implant procedure and are followed for 12 months.

The Major EMPOWER MPS System- and Procedure-related CFR from the date of the EMPOWER PG implant procedure through 365 days post implant will be calculated using Kaplan-Meier methodology.

The 97.5% one-sided lower pointwise confidence limit of the Major EMPOWER MPS System- and Procedure-related CFR will be calculated via log-log methodology and compared to the performance goal of 81%. If the lower confidence limit exceeds 81%, the null hypothesis will be rejected.

The Kaplan-Meier methodology was chosen for this endpoint to utilize all available data for each subject. To assess the robustness of this analysis method and the potential impact missing data could have had on the analysis results, a tipping point analysis will be conducted that will include subjects with the EMPOWER PG implanted and the attempted subjects. The tipping point analysis will assign each subject with missing data as either having or not having a Major EMPOWER MPS System- and Procedure-related Complication. All possible combinations of these subjects' data will be evaluated along with the actual observed data to find the point, if any, at which the endpoint is failed.

#### 11.1.3 Secondary Safety Endpoint: All-Cause Survival from Implant through 2 Years Post-Implant

The Secondary Safety Endpoint will be assessed for all implant subjects. Safety will be confirmed by evaluating the 2-Year all-cause survival rate post implant. Deaths due to any reason will count against this endpoint. Data from this endpoint will be used to evaluate the longer-term safety of the EMPOWER PG for the purposes of obtaining CMS approval and Medicare reimbursement. This analysis will be performed when all implanted subjects have been followed for a minimum of 730 days. In order to control the overall study Type I error rate, this endpoint will only be evaluated if Safety Endpoint 1,the primary effectiveness endpoints, and the Secondary Effectiveness endpoint are successful.

#### 11.1.3.1 Hypotheses

The following hypotheses will be used to evaluate the Secondary Safety Endpoint:

H0: The all-cause survival rate through 2 years post-implant  $\leq 85\%$ 

HA: The all-cause survival rate through 2 years post-implant > 85%.

#### 11.1.3.2 Sample Size

A sample size of 123 implanted subjects followed for 2 years is required to evaluate the Secondary Safety Endpoint. This sample size was calculated based on a one-sided normal approximation for a single binomial proportion, using SAS Version 9.4 with the following assumptions:

- Performance goal = 85%
- Significance level = 2.5% one-sided
- Power = 80%

Given an expected attrition rate of 40%, 275 subjects are needed, which is less than the 300 enrolled subjects. This means that the overall study sample size is not being driven by this endpoint.

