# 9 Subject Accountability

#### 9.1 Point of Enrollment

Subjects will be considered enrolled into the MODULAR ATP Clinical Study at the time of Informed Consent Form (ICF) execution. All subject enrollments will be counted against the enrollment ceiling for the study.

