#### 11.1.1.2 Sample Size

A group sequential design based on the z test of a binomial proportion will be used to assess the Safety Endpoint 1. The assumptions and parameters pertaining to this endpoint are as follows:

- Performance Goal: 86% Major EMPOWER MPS System- and Procedure-related CFR through 6 months post-implant
- Attrition: 25% of enrolled subjects through the 6-month visit
- Power = 90%
- Alpha < 2.5% (1-sided)
- Alpha boundary determination: A power error spending function will be used with  $\rho=1.5$

#### • Number of analyses: 2

• Timing of analyses: The single interim endpoint analysis will occur after a minimum of 134 subjects who have undergone any portion of the EMPOWER PG implant procedure have been followed for 6-months (based on a required 0.6 Information Fraction for the interim analysis). The final analysis of this endpoint may occur when 223 subjects who have undergone any portion of the EMPOWER PG implant procedure have been followed for 6-months if the null hypothesis of Safety Endpoint 1 is not rejected at the interim analysis.

Based on these assumptions and parameters, a sample size of 134 subjects is required for the interim analysis with an alpha of 1.2%. If the null hypothesis is not rejected at the interim analysis, a sample size of 223 subjects is required for the final analysis with an alpha of 1.9%.

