#### 11.1.4 Primary Effectiveness Endpoint 1: Communication Success between the S-ICD and EMPOWER PG at the 6 Month Visit

Primary Effectiveness Endpoint 1 will be assessed at the time of the interim analysis of Safety Endpoint 1 if its null hypothesis is rejected, or at the final analysis if its null hypothesis is not rejected at the interim analysis (refer to **Section 11.3**). The assessment will include subjects who are successfully implanted with both the EMPOWER PG and S-ICD. Effectiveness will be confirmed by evaluating the communication between S-ICD and the EMPOWER PG in four postures: upright, supine, and right and left side. The test unit for this endpoint will be the result from each posture. Communication success will be defined as any evidence of a paced beat during communication testing in a given posture at the initial programmed communication Programmed Telemetry Setting.

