#### 11.1.6.2 Sample Size

A minimum of 35 usable datasets is required to sufficiently power the Secondary Effectiveness Endpoint. A usable dataset is defined as one for which the subject completes at least treadmill Stage 4 without continuous use of the treadmill handlebars in either treadmill Stage 3 or Stage 4, as described further in Document 92614291 (provided separately).

Sample size estimates were obtained using two one-sided t-tests (TOST).

The sample size of 35 usable datasets was calculated using the following assumptions:

- Performance goals = mean slope between 0.65 and 1.35
- Expected standard deviation = 0.35
- One-sided significance level = 2.5%
- Power = 90%

Assuming that 40% of subjects will not have usable datasets, at least 59 subjects will be included in the treadmill test in order to obtain at least 35 usable datasets.

The sample size for this study was not determined by this endpoint.

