#### 11.4 Sample Size Summary

The study will enroll up to 300 subjects, which is approximately what is required for the sample size of the final analysis of Safety Endpoint 1, 223 subjects followed for 6 months or 298 subjects enrolled and accounting for an estimated 25% attrition rate ( $223 \approx 298 \times 75\%$ ).

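### Section 11.1.3.2: 123 implanted subjects and 40% attrition give 205 subjects, not the stated 275

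*Protocol*

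**What the plan says.** Protocol Section 11.1.3.2 sets the evaluable number: "A sample size of 123 implanted subjects followed for 2 years is required to evaluate the Secondary Safety Endpoint". The method is given as "This sample size was calculated based on a one-sided normal approximation for a single binomial proportion, using SAS Version 9.4", with a performance goal of 85%, a one-sided 2.5% significance level and 80% power. The section then moves from evaluable subjects to subjects needed: "Given an expected attrition rate of 40%, 275 subjects are needed, which is less than the 300 enrolled subjects". It concludes that this endpoint does not determine the study size. Apart from the 40%, no loss factor is named.

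The protocol's way of allowing for attrition is visible elsewhere:

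- Section 11.4 gives "223 subjects followed for 6 months or 298 subjects enrolled and accounting for an estimated 25% attrition rate" and writes the relation out as 223 ≈ 298 × 75%.
- Section 11.1.1.2 says what the 25% is a share of: "Attrition: 25% of enrolled subjects through the 6-month visit".
- Section 11.1.6.2, for the rate-response endpoint, which needs 35 usable datasets, says: "Assuming that 40% of subjects will not have usable datasets, at least 59 subjects will be included in the treadmill test".

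**The concern.** Both inputs to the step are printed in the same short section, and the printed result is 70 subjects above what they give. The difference is too large to be rounding. The endpoint is formally tested, as the last step of the gated sequence in Section 11.5.1, and Section 11.1.3 says its data are meant to support CMS approval and Medicare reimbursement. Its enrolment need should therefore be reproducible from its own inputs. As the text stands, a reader cannot tell whether the 123, the 40% or the 275 is out of step, nor how much loss to follow-up the endpoint was planned to absorb.

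**Working it through.** **Inputs (Section 11.1.3.2).** Evaluable n = 123 implanted subjects followed for 2 years; attrition d = 40%; stated need = 275; enrolment = 300.

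**Check of the protocol's convention.** The formula is N = n/(1 − d), rounded up. The stated results come from the synopsis statistical table unless noted.

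| Endpoint | n | d | n/(1 − d) | Stated |
|---|---|---|---|---|
| Safety 1, interim | 134 | 25% | 178.7 → 179 | 179 |
| Safety 1, final | 223 | 25% | 297.3 → 298 | 298 |
| Safety 2 | 112 | 30% | 160 | 160 |
| Primary Effectiveness 1 | 38 | 30% | 54.3 → 55 | 55 |
| Primary Effectiveness 2 | 57 | 30% | 81.4 → 82 | 82 |
| Secondary Effectiveness (Section 11.1.6.2) | 35 | 40% | 58.3 → 59 | 59 |
| **Secondary Safety (Section 11.1.3.2)** | **123** | **40%** | **205** | **275** |

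Section 11.1.2.3 uses the same relation in reverse: 300 × 0.70 = 210. Only the last row of the table fails.

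**Other routes from 123 and 40%.** The common mistaken formula, n × (1 + d), gives 123 × 1.40 = 172.2 → 173. That does not give 275 either.

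**What 275 would imply.**

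- At 40% attrition: 275 × 0.60 = 165 evaluable subjects, not 123.
- From 123 evaluable: 1 − 123/275 = 55.3% attrition, not 40%.
- With 123 and 40% both kept: a further loss of 1 − 205/275 = 25.5%.

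**Possible origin of 165 (assumption).** The text available does not show the expected 2-year survival rate. If it is assumed to be 93%, the one-sample normal approximation at one-sided 2.5% gives 165 at 90% power, and 165/0.60 = 275. At the stated 80% power it gives 131, and 131/0.60 = 218.3 → 219. To give 123 at 2.5% and 80% power, the assumed survival would have to be about 93.2%. So 275 may be left over from a 90%-power calculation, but the documents do not establish this.

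**Effect on the study-size statement.** Both 205 and 275 are below 300. The number left from 300 enrolled, against the number required, is:

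- 123 and 40% correct: 300 × 0.60 = 180, which is 57 above 123.
- 165 intended at 40%: 180, which is 15 above 165.
- Larger total loss intended: 300 × 123/275 = 134, which is 11 above 123.

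The endpoint fits within 300 on each reading.

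**The case against.** The strongest defence is that 275 includes a second loss, between consent and implant. The 123 are implanted subjects, the 275 is compared with enrolled subjects, and enrolment is the wider group: "All subject enrollments will be counted against the enrollment ceiling for the study". Subjects classified as Intent or Attempt under Section 9.2 count as enrolled and are then withdrawn. Applying the 25% used for Safety Endpoint 1 on top of the 40% gives 123/0.60/0.75 = 273.3 → 274, one short of 275.

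This shows that 275 could be right but unexplained. It does not rescue the text. No such step or rate is written, and the near match is not exact. The 25% is itself defined on enrolled subjects through 6 months, so compounding it with a 2-year rate would probably count some losses twice. Primary Effectiveness Endpoint 1 is also restricted to implanted subjects ("The assessment will include subjects who are successfully implanted with both the EMPOWER PG and S-ICD"), yet it goes from 38 to 55 with 30% alone.

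Three further points limit the weight of the finding:

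- The 40% for the treadmill test is a share of tested subjects without usable data, not loss over 2 years. It supports the formula, not the rate.
- Of the two figures 275 is the more cautious, so it cannot lead to under-enrolment.
- The margins of 57, 15 and 11 are head counts, not power. The Kaplan-Meier analysis in Section 11.1.3.3 also uses subjects censored before 730 days.

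**Conclusion.** The concern holds, as a minor point. From 123 and 40% the protocol's own formula gives 205; the stated 275 is 70 higher and does not follow from the figures shown. This rests only on numbers printed in Section 11.1.3.2 and on the convention seen in every other endpoint; it does not depend on the unshown survival assumption. Which of the three figures is out of line cannot be settled from the documents. Planned enrolment of 300, which Section 11.4 bases on Safety Endpoint 1, is unaffected, and so is the statement that this endpoint does not drive the study size.

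**What to change.** Make Section 11.1.3.2 follow from one calculation:

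- If 123 and 40% stand, replace 275 with 205.
- If a loss from enrolment to implant was intended, state it with its rate, so that 123, both rates and the final number agree.
- If the attrition rate is wrong, correct it; 275 from 123 corresponds to about 55%.
- If the evaluable number should be 165, correct it together with the power or the assumed survival rate, because 123 is the number tied to the stated 80% power.

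The first three options cost one or two figures or one added clause, with no effect on alpha, power, analysis set or enrolment. The fourth also restates a design assumption but still needs no added subjects, since 165/0.60 = 275 is below 300.

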#### 11.1.3.3 Statistical Methods

Endpoint analysis will be performed on all implanted subjects.

The survival rate from the implant through 730 days post-implant will be calculated using Kaplan-Meier methodology. Deaths for any reason will count as an event for this endpoint. The 5% one-sided lower pointwise confidence limit of the survival rate will be calculated via log-log methodology and compared to the performance goal of 85%. If the lower confidence limit exceeds 85%, the null hypothesis will be rejected.

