#### 9.2.2 Attempt

Attempt - refers to a subject who 1) has been enrolled in the MODULAR ATP Clinical Study, 2) has had anesthesia administered in preparation for the surgical implant procedure of an EMPOWER PG and/or S-ICD, but 3) is not successfully implanted with the EMPOWER PG and/or S-ICD.

Attempt subjects must be followed at least 30 days (either in-clinic or phone contact) post-attempted EMPOWER PG and/or S-ICD device implant to assure there are no associated adverse events or to assure the resolution of any adverse events associated with the attempted S-ICD and/or EMPOWER PG device implants. Attempt subjects will be included in the data analysis for the implant success rate. Attempt subjects must be withdrawn from the study after satisfying the follow-up of at least 30 days from attempted device implant.

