#### 9.2.3 Partial Implant

**Partial Implant** - refers to a subject who 1) has been enrolled in the MODULAR ATP Clinical Study, 2) has had either the S-ICD System introduced into their subcutaneous space or the EMPOWER MPS introduced into their vasculature, 3) is successfully implanted with either the S-ICD System or EMPOWER PG device, **but not both**, AND 4) is unable to or for whom there is no intention to implant the full mCRM Coordinated System.

Subjects classified as a Partial Implant that are implanted with an EMPOWER PG must be followed according to this protocol, with all relevant EMPOWER PG device data and
testing collected. Time 0 for the purpose of determining timing of follow ups for these subjects is the day it is determined the S-ICD will not be implanted.

Note that subjects implanted with an S-ICD System (prior to upgrading with clinical firmware in the MODULAR ATP Clinical Study) who are not implanted with an EMPOWER PG may be withdrawn from the MODULAR ATP Clinical Study after satisfying the follow-up of at least 30 days from S-ICD device implant.

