## 9.2.4 Implant

**Implant** - refers to a subject who has been enrolled in the MODULAR ATP Clinical Study and is successfully implanted with the S-ICD **and** EMPOWER PG device per the study protocol (this includes those subjects previously implanted with an S-ICD System). Implant subjects are followed in accordance with the follow-up schedule included in this protocol and included in analyses of safety, effectiveness, and performance based on provisions discussed in **Section 11**.

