### 11.1.1.3 Statistical Methods

Endpoint analysis will be performed on data from subjects that have undergone any portion of the EMPOWER PG implant procedure, including subjects that do not have the EMPOWER PG successfully implanted. The major EMPOWER MPS System and Procedure-related CFR from the date of the EMPOWER PG implant procedure through 6 months (180 days) post-implant will be calculated using Kaplan-Meier methodology.

The interim analysis will be conducted once 134 subjects have undergone the EMPOWER PG implant procedure and have been followed for 6 months (180 days). Using the allocated alpha level of 1.2% for the interim analysis, the 98.8% one-sided lower pointwise confidence limit of the Major CFR will be calculated via log-log methodology and compared to the performance goal of 86%. If the lower confidence limit exceeds 86%, the null hypothesis will be rejected.

If the interim analysis does not result in the rejection of the null hypothesis, the final analysis will be conducted once 223 subjects have undergone the EMPOWER PG implant procedure and have been followed for 6 months (180 days). Using the allocated alpha level of 1.9% for the final analysis, the 98.1% one-sided lower pointwise confidence limit of the Major CFR will be calculated via log-log methodology and compared to the performance goal of 86%. If the lower confidence limit exceeds 86%, the null hypothesis will be rejected.

The Kaplan-Meier methodology was chosen for this endpoint to utilize all available data for each subject. To assess the robustness of this analysis method and the potential impact missing data could have had on the analysis results, a tipping point analysis will be conducted that will include subjects that have undergone any portion of the EMPOWER PG implant procedure, including subjects that do not have the EMPOWER PG successfully implanted. The tipping point analysis will assign each subject with missing data as either having or not having a Major EMPOWER MPS System- and Procedurerelated complication. All possible combinations of these subjects' data will be evaluated along with the actual observed data to find the point, if any, at which the endpoint is failed.

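### The two-year survival endpoint leaves out failed EMPOWER attempts and names neither device nor start date, so some early deaths may not count

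*Protocol*

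**What the plan says.** Protocol 11.1.3 states the population as follows: "The Secondary Safety Endpoint will be assessed for all implant subjects". The statistical methods in 11.1.3.3 repeat it in slightly different words: "Endpoint analysis will be performed on all implanted subjects". Survival is estimated by Kaplan-Meier from the implant through 730 days, deaths from any cause count, and the lower log-log limit is compared with 85%. The stated purpose is the longer-term safety of the EMPOWER PG, for CMS approval and Medicare reimbursement. Neither section names the device or the date at which the clock starts.

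Section 9.2 sorts enrolled subjects into classes. An Implant subject "is successfully implanted with the S-ICD and EMPOWER PG device per the study protocol". An Attempt subject "is not successfully implanted with the EMPOWER PG and/or S-ICD"; these subjects are followed for at least 30 days and then withdrawn. A Partial Implant has one device but not both. For those with the pacemaker, "Subjects classified as a Partial Implant that are implanted with an EMPOWER PG must be followed according to this protocol".

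Safety Endpoint 1 uses a wider set (11.1.1.3): "Endpoint analysis will be performed on data from subjects that have undergone any portion of the EMPOWER PG implant procedure". Safety Endpoint 2 does the same and adds, in 11.1.2.4, that this means "i.e., both implant and attempt subjects". Both run from the EMPOWER PG procedure date. The SAP text does not take up the population or the clock for the survival endpoint.

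**The concern.** An all-cause survival rate is meant to count every death after exposure to the procedure. Here a subject must first be classed as implanted. Someone who dies during or soon after an unsuccessful EMPOWER attempt never enters the denominator or the event count.

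If Implant means both devices, entry also depends on living until the second procedure. Section 10.3 recommends placing the EMPOWER PG first in subjects who need both, does not require the same day, and strongly recommends completing both within 30 days of enrollment. Section 10.3.4 sets Time 0 at the date both are in place. Under that definition neither start date repairs the problem. Starting at Time 0 drops the interval between procedures. Starting at the EMPOWER date keeps the interval but fills it only with subjects who survived it (immortal time).

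At stake is a formally tested endpoint that could pass slightly too easily, and a set and clock that two analysts could build differently from the same text.

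**Working it through.** **1. Who is in the set under each reading**

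| Subject | Safety Endpoints 1 and 2 | Survival endpoint, EMPOWER PG in place | Survival endpoint, both devices (9.2.4) |
|---|---|---|---|
| Failed EMPOWER attempt | in | out | out |
| EMPOWER-only Partial Implant | in | in | out |
| Dies after EMPOWER, before a staged S-ICD | in | in | out |
| Both implanted in one session | in | in | in |
| Existing compatible S-ICD, EMPOWER implanted | in | in | in |

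The first row holds under both readings. The second and third depend on what Implant means.

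**2. Inputs**

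From 11.1.3.2: goal 85%, one-sided significance level 2.5%, 123 subjects followed for two years, and 275 subjects after allowance for 40% attrition. The expected two-year survival is not in the available text, so 123 cannot be reproduced directly. Solving the usual normal-approximation formula backwards at 2.5% and 80% power gives about 93.2%, so 123 is attainable. Taking 123/0.6 gives 205 rather than 275. That is a separate matter, and the two figures in the plan are used here as bounds.

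Assumptions: no censoring, and a share d of all subjects with an EMPOWER procedure who die before they can be classed as implanted. The documents give no value for d; 0%, 1% and 2% are shown.

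**3. Pass rule**

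With x deaths among n subjects, S = 1 − x/n and the one-sided lower log-log limit is

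L = S^exp( z·√(x/(n(n−x))) / |ln S| ), with z = 1.96.

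The endpoint passes if L > 0.85.

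- n = 123: 10 deaths give L = 0.854 (pass), 11 give 0.844 (fail).
- n = 275: 29 deaths give L = 0.852 (pass), 30 give 0.848 (fail).

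**4. Effect of removing early deaths**

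If true survival over all procedure subjects is 85% and a share d die before classification, survival in the analysed set is 0.85/(1−d): 85.0% at d = 0, 85.9% at 1%, 86.7% at 2%. The false-pass probability is the binomial probability of at most 10 (or 29) deaths at that rate.

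| d | n = 123 | n = 275 |
|---|---|---|
| 0% | 1.7% | 2.0% |
| 1% | 3.1% | 4.8% |
| 2% | 5.4% | 10.5% |

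Section 11.1.3.3 states a 5% one-sided limit where 11.1.3.2 states 2.5%. With a 5% limit the pass counts become 11 of 123 and 31 of 275. The rows then read 3.3%, 5.7%, 9.6% for n = 123 and 4.6%, 9.8%, 18.9% for n = 275. The levels are higher and the direction is the same.

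**5. The same point in deaths**

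Assume 300 procedure subjects with 15 (5%) outside the both-device set, at the 2.5% limit. The analysed 285 pass with at most 30 deaths; all 300 pass with at most 32. Starting from 30 of 285, three uncounted deaths (33 of 300) turn a pass into a fail, while the point estimate moves only from 89.5% to 89.0%.

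**The case against.** Section 11.1.3 never says both devices. Where the plan wants that set it says so, as in 11.1.4 for Primary Effectiveness Endpoint 1. The wording "i.e., both implant and attempt subjects" in 11.1.2.4 stands for everyone with an EMPOWER PG procedure, which suggests that implant there means the pacemaker alone. The stated purpose is also the EMPOWER PG. This stands: the both-device reading is the natural one given 9.2.4, but it is not stated, so exclusion of EMPOWER-only subjects and of deaths between procedures is conditional. A reader might infer that the plan definitely restricts the endpoint to subjects with both devices; the documents do not settle that.

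A reader might also infer that procedure-related deaths cannot count against this endpoint. That is not supported either. Such deaths count once the subject is classed as implanted, which includes same-session implants and subjects with an existing compatible S-ICD. Deaths adjudicated as related to the EMPOWER system or procedure count in Safety Endpoint 1 to 180 days and Safety Endpoint 2 to 365 days, over everyone with any portion of the procedure. The Clinical Events Committee reviews all subject deaths (21.2). No death is hidden from the study.

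Finally, survival among device recipients can be defended for a longer-term question. The endpoint is tested only after Safety Endpoint 1, both primary effectiveness endpoints and the Secondary Effectiveness Endpoint succeed, and study success does not depend on it (11.5.1). That limits the consequence. It does not explain why failed attempts are left out, and it does not supply the missing device and date.

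**Conclusion.** The point holds in a limited form. Deaths after a failed EMPOWER attempt are outside the survival rate whether implanted means the EMPOWER PG or both devices. Deaths in EMPOWER-only subjects and between staged implants are outside it only if Implant has its 9.2.4 meaning. The device and the start date are unspecified in either case.

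Any bias is upward, confined to this one all-cause survival rate, and probably small. The false-pass figures are illustrations: they rest on assumed shares of 1% and 2% dying before classification, no censoring, and a one-sided 2.5% limit. They do not estimate what will happen in this trial. The matter is a minor one, worth correcting because the plan already contains the right population and clock.

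**What to change.** In 11.1.3 and 11.1.3.3, define the analysis set as all subjects who undergo any portion of the EMPOWER PG implant procedure, with time zero at that procedure date, as for Safety Endpoints 1 and 2. Report the both-device set, counted from Time 0, as a supportive analysis. If the sponsor prefers a narrower primary set, name the device or devices and the start date, and give the wider set as a sensitivity analysis.

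The cost is about one sentence in each place and no new visits, since EMPOWER-only subjects are already followed on schedule. The survival estimate may be slightly lower. Attempt subjects would be censored at withdrawal after at least 30 days, so for them only early deaths would register; those are the deaths now missed.
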